### **DESIGN:**

This is a Phase II placebo-controlled randomized, blinded, feasibility trial.

The multisite study will consist of 80 infants (n=40 in each arm)  $\geq$ 34 week GA infants with NE who **DO NOT** qualify for hypothermia therapy, that will be randomized to receive either Darbe,

## **MEND (Mild Encephalopathy in the Newborn treated with Darbepoetin)**

11.18.2020

(10 µg/kg IV), or placebo. **We plan to enroll 20 participants at the University of New Mexico.** A total of 80 infants at all sites (see table below) will be enrolled.

[name] (PI) Holds the IND for Darbepoetin and mild NE (IND 132207) and will remain as a study team member and overall PI of this multi-center study. Treatment will be randomized by the pharmacy and blinded to the caregivers. All groups will receive the dose within 24 hours of birth.

✓		Intervention
Experimental groups Darbe	N=40	10 mcg/kg/dose Darbe IV <24 hours of age
Control group Placebo	N=40	Normal saline placebo dose IV at <24 hours of age

### **STUDY PROCEDURES:**

#### **Timeline for the study:**

Anticipated time to recruit 80 patients will be 2 years. Centers that will participate in this Phase II study will include University of New Mexico Children's Hospital, University of Utah Medical Center, Intermountain Medical Center, Primary Children's Medical Center, The University of South Florida, Stanford University, and University of Texas Southwestern.

Once the infant meets eligibility criteria and consent has been obtained from the parent(s), the infant is a study participant.

#### **Data collection**

At study entry maternal demographics, specifically: age, education, race, ethnicity will be collected. A modified Sarnat exam will be repeated at discharge, transfer, or 96 hours of age (which ever occurs first) and documented. We will collect vital signs, MRI, hemoglobin/hematocrit, CBC with differential, liver function tests, and complete physical exam if they are done as indicated by clinical care. MRIs done for clinical indication will be de-identified and sent to a pediatric neuroradiologist for a centralized read. Once de-identified, these will be sent via CD or Lifelimages to UT Southwestern where they will be read by the neuroradiologist. We are requesting waiver of consent to send de-identified MRIs to UT Southwestern for an additional reading. All MRIs have been and will be ordered per clinical indication and are not required under the study protocol.

#### **Immunogenicity Testing**

The vast majority of babies admitted to the NICU have a CBC with diff drawn on admission. If there is at least 0.5mL of blood remaining (scavenged blood) after analysis, we will collect that blood and use as our baseline sample for potential immunogenicity testing. If the baby remains in the NICU for 2 weeks and has a blood test done for clinical reasons, we will attempt to keep 0.5mL (scavenged blood). Additionally, a letter (attached) will be given to the PCP stating that the patient is

enrolled in a research study. If there are concerns for anemia and the PCP orders a CBC within the first year of life we will ask for 0.5mL of blood (scavenged blood). We will ask the lab to hold “scavenged” blood and store for up to 6 months beyond enrollment of the last patient.

#### PK Sampling

Blood samples will be used to establish population pharmacokinetics. Scavenged blood samples of 0.05 mL of blood will be collected from all clinical blood draws throughout the infant’s hospitalization and sent to the University of Iowa for population pharmacokinetics using meso-scale discovery assay to detect Epo levels. Since a baseline sample is also required for immunogenicity testing we will collect an extra 0.3 mL of blood with the “pre-drug” blood work drawn in the NICU. Study participants will have the option of opting in for this additional blood draw. This will ensure that there is enough blood for potential immunogenicity testing and pK analysis. Every effort will be made to obtain this sample with a blood draw that is needed for clinical purposes (such as a glucose check). All other pk samples will be off of scavenged blood. Parents will be given the option to opt into this part of the study on the consent form.

Parents of participants will be contacted by phone call at 4 months of age which will include developmental screening via a modified Ages and Stages questionnaire (attached), number of hospitalizations, seizures, need for assisted respiratory support, failure to thrive, medication use, use of early intervention services, hearing impairment, any concern with vision.

Participants will have neurodevelopmental testing (Bayley III and Gross Motor Function Assessment) performed at 8-12 months of age. We will also conduct a brief medical exam including weight, length, head circumference, blood pressure, and heart rate.

In addition, we may contact the child’s primary care provider and ask for the baby’s most recent medical history and the result of the most recent hematocrit.

Data will be kept for analysis for up to 10 years.

#### **Standard of Care vs. Research-Related Procedures:**

Research-Related procedures:

1. Study drug can be given as soon as the infant is found to **NOT** qualify for TH but before 24 hours of age.
2. Extra 0.3 mL of blood drawn prior to drug administration (optional)
3. Neurological examination at discharge, transfer, or 96 hours of age (which ever occurs first)
4. Follow up phone calls at 4 months of age
5. Bayley Scales of Infant Development examination at 8-12 months corrected age.
- 6.

## **MEND (Mild Encephalopathy in the Newborn treated with Darbepoetin)**

11.18.2020

7. Weight, length, head circumference, heart rate, and blood pressure at 8-12 months.
8. Medical records from primary care provider including hemoglobin and hematocrit if available when indicated.

Standard of Care:

1. Monitoring and routine supportive care.

### **Safety**

For the purpose of this study, an **adverse event** (AE) will be defined as any adverse change from the patient's baseline condition that occurred following the administration of the study drug through the end of the study period. Safety will be evaluated during the first 7 days of life or until hospital discharge (whichever comes first) by documenting potential adverse events such as (but not limited to) alterations in blood pressure, secondary infections, neutropenia, thrombotic/vascular events, hematologic events (platelets, Hct level, polycythemia), and hepatic/renal function that are outside of normal range for the study population.

We will assess for the rare complication (1 in 10,000 in adults with renal failure) of pure red blood cell aplasia. The vast majority of babies admitted to the NICU have a CBC with diff drawn on admission. If there is at least 0.5mL of blood remaining (scavenged blood) after analysis, we will collect that blood and use as our baseline sample. Similarly, most babies admitted to the NICU have electrolytes or bilirubin levels drawn at 24-72 hours of age, if there is at least 0.5mL of blood remaining (scavenged blood) after analysis, we will collect that blood and use as our second sample. If the baby remains in the NICU for 2 weeks (uncommon) and has a blood test done for clinical reasons, we will attempt to keep 0.5mL (scavenged blood) to assess for pure blood cell aplasia. Additionally, a letter (attached) will be given to the PCP stating that the patient is enrolled in a research study. If there are concerns for anemia and the PCP orders a CBC within the first year of life we will ask for 0.5mL of blood (scavenged blood). We will ask the lab to hold "scavenged" blood and store for up to 6 months beyond enrollment of the last patient.

We will also ask for the medical records from the child's primary care provider and their most recent hematocrit/hemoglobin.

**Long Term Safety** will involve phone calls at 4 months of age which will include developmental screening via Ages and Stages questionnaire, hospitalizations, seizures, need for assisted respiratory support, failure to thrive, medication use, use of early intervention services, hearing impairment, any concern with vision. In addition we will contact the child's primary care provider and ask for the child's medical records and most recent hematocrit/hemoglobin to assess for safety.

**Serious adverse events** (SAE) will be defined as any event that results in: death, a life threatening event (major venous thrombosis, stroke, and/or severe hypertension), persistent or significant disability/ incapacity, and/or prolongs inpatient hospitalization.

SAEs will be reported until 30 days following final cessation of therapy or until hospital discharge, whichever comes first.

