## **7. Withdrawal of Subjects**

This is a single intervention study. If the infant is eligible and consented then the study drug will be given. After the delivery of the drug the intervention is complete. The family may choose to withdraw from the study at any time. Follow-up phone calls and neurodevelopmental testing will occur between 4-12 months of age.

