## 12. Economic Burden to Subjects

Research Procedures	Number of Samples/Procedures	Responsible Party	
		Study	3 rd Party Payer or Participant
Darbepoetin 10 micrograms/kg	1		
Neurodevelopmental Testing	1		
Follow up phone calls	2		
Antibody testing	2		
Pk Testing (non scavenged blood)	1		
Pk Testing (scavenged blood)	2-10		
_____	_____		
_____	_____		
Standard of Care Procedures	Number of Samples/Procedures	Responsible Party	
		Study	3 rd Party Payer or Participant
Routine neonatal care	_____		
_____	_____		
_____	_____		
_____	_____		
_____	_____		
_____	_____		
_____	_____		
_____	_____		

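### The 24-72 hour "second sample" falls at most 3 days after the only dose and should not count as post-dose antibody evidence; later samples are conditional, and the sections disagree on which are tested

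*Combined protocol and SAP*

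**What the plan says.** The Safety text in Section 3 sets the purpose: "We will assess for the rare complication (1 in 10,000 in adults with renal failure) of pure red blood cell aplasia". It then lists the blood to be used. The baseline is leftover blood from the admission blood count. Next, because "most babies admitted to the NICU have electrolytes or bilirubin levels drawn at 24-72 hours of age", leftover blood from those draws is kept if at least 0.5 mL remains: "we will collect that blood and use as our second sample". After that come two conditional samples. One applies "If the baby remains in the NICU for 2 weeks (uncommon) and has a blood test done for clinical reasons". The other applies in the first year of life if there is concern about anemia and the primary care provider orders a blood count. The text also asks the primary care provider for records and the latest hematocrit or hemoglobin.

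On dosing, the Design text in Section 3 states "All groups will receive the dose within 24 hours of birth", and Section 7 adds "After the delivery of the drug the intervention is complete".

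The Immunogenicity Testing text in Section 3 gives a shorter list. It has the same baseline, then goes straight to the later stay: "If the baby remains in the NICU for 2 weeks and has a blood test done for clinical reasons, we will attempt to keep 0.5mL". It then gives the first-year sample. The 24-72 hour sample is absent.

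The table in Section 12 has a line for "Antibody testing" with a count of 2 and no time points.

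**The concern.** A post-dose antibody sample is useful only if it is drawn after an antibody could have formed. Here the only post-dose sample that the plan expects in most infants is tied to routine draws in the first three days of life, and the dose itself may be given late on the first day. An infant dosed at hour 23 and bled at hour 24 has, in effect, two baseline samples.

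If that sample fills the post-dose slot, an infant can be counted as assessed for induced antibody without any blood that could have shown one. Section 5 says that this pilot's data will be used to power a large multicenter trial. A safety statement with the wrong denominator could be carried into that trial.

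**Working it through.** The plan gives no sample size or error rate for this assessment, so there is no stated figure to reproduce. The check has four steps.

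**1. Interval from dose to second sample.** Inputs: dose at age 0 to just under 24 h (Section 3, Design); sample at age 24 to 72 h (Section 3, Safety). Interval = sample age minus dose age.
- Shortest: 24 h minus just under 24 h = just above 0 h.
- Longest: 72 h minus 0 h = 72 h, or 72/24 = 3 days.

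There is no second dose, so the sample cannot be read as following an earlier exposure.

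**2. The sections side by side.**

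| Sample | Safety | Immunogenicity Testing | Condition |
|---|---|---|---|
| Baseline (admission) | yes | yes | enough blood left over |
| 24-72 h of age | yes, as the second sample | not listed | enough blood left over |
| 2 weeks | yes, called uncommon | yes | still in the NICU and a clinical blood test done |
| First year | yes | yes | concern for anemia and a blood count ordered |

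Section 12 funds two antibody tests and does not say which rows they are for. No section says how an early negative will be read, and none plans a late sample for every infant. Routine safety capture does not fill the gap. Adverse events are evaluated for 7 days or until discharge, whichever is first. Serious events are reported for 30 days after therapy or until discharge, whichever is first.

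**3. What a small late-sampled group can show.** The number of treated infants with a sample at 2 weeks or later is not given. I assume 5%, 10% or 20% of the 40, that is 2, 4 or 8 infants, and compare with all 40.
- Upper limit: with no positives among m infants, the exact one-sided 95% upper limit is 1 - 0.05^(1/m).
- Detection: for an assumed true antibody rate r and late-sampled share s, the chance of at least one positive is 1 - (1 - r x s)^40. The rates r are illustrative.

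| Late-sampled share (m) | Upper limit, no positives | r = 1% | r = 5% | r = 10% |
|---|---|---|---|---|
| 5% (2) | 78% | 2.0% | 9.5% | 18% |
| 10% (4) | 53% | 3.9% | 18% | 33% |
| 20% (8) | 31% | 7.7% | 33% | 55% |
| 100% (40) | 7.2% | 33% | 87% | 98.5% |

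Reporting no positives among 40 when only 4 had an informative sample would put the upper limit at 7.2% instead of 53%.

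**4. The rare event itself.** At the cited 1 in 10,000, the chance of at least one case among 40 treated infants is 1 - 0.9999^40 = 0.40%. Even with all 40 fully assessed and no case, the upper limit of 7.2% is about 720 times the cited rate (0.0722/0.0001 = 722). No sampling schedule changes that. It limits what the trial may claim and is not an argument about timing.

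**The case against.** The strongest reply is that the plan never calls the 24-72 hour blood an antibody sample. In the Safety paragraph the aplasia purpose is attached in so many words only to the 2-week blood. The Immunogenicity Testing text leaves the early sample out. That text and the PK Sampling text describe the testing as potential, and Section 18 has samples sent at study completion for immunogenicity and/or PK work. This fits storing early blood as a comparator in case anemia appears later, which does no harm. The plan also has a clinical route to aplasia: the letter to the primary care provider, the anemia-prompted sample, the later hematocrit or hemoglobin, and the 8-12 month visit with hematology as available. Immunogenicity is not among the specific aims, and the proposed change yields no additional late blood.

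Much of this stands, and it rules out several stronger readings that a reader might infer:
- That early negatives will be reported as absence of antibody. No section gives any reporting rule.
- That the two funded tests are the baseline and 24-72 hour pair. Section 12 gives no time points; under the Immunogenicity Testing list the pair would be baseline and a later sample.
- That sampling time is all that matters and the aplasia assessment fails as a whole. The later hematocrit or hemoglobin is also informative.
- That circulating drug would spoil the early test. No antibody assay is described. The half-lives in Section 2 come from a different population, cooled infants with moderate to severe encephalopathy.

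The reply does not remove the core. The Safety paragraph opens with the aplasia purpose and labels a baseline and a second sample under it. Someone following that text may spend the second test on near-baseline blood and count the infant as assessed. The clinical route is incomplete too: the list of research procedures in Section 3 limits the primary-care values to what is available when indicated, and no earliest date is set.

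**Conclusion.** The point holds in a limited form. The second sample named for the aplasia assessment falls just above 0 to at most 72 hours after the only dose. A negative result on it is not evidence against a drug-induced antibody. This rests on one assumption from general immunology that the documents do not state: a new antibody to a first exposure does not appear within 3 days.

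Both later samples are conditional, so most infants without symptoms may have no informative post-dose antibody sample, and the pilot could count as assessed infants who were not. How many is unknown; the assumed range of 2 to 8 of 40 only shows how far the upper limit moves. False reassurance is a risk that the text leaves open, not an outcome that it prescribes.

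The primary outcome and the randomized comparison are not affected. What changes is the safety statement that the trial can support. That is enough to correct the text, since the sections must be reconciled in any case.

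**What to change.** Reconcile Section 3 (Safety and Immunogenicity Testing) with Section 12, so that all three name the same samples and say which two are antibody-tested. In the reconciled text:
- State that the 24-72 hour sample does not count as post-dose antibody evidence. It may be kept as a stored comparator or for PK.
- Assign the second funded test to the latest scavenged sample taken at about 2 weeks of age or later. These are the 2-week and first-year samples already planned.
- Report, by arm, the number of infants with such a sample, and use it as the denominator for any antibody result.
- For all other infants, report only primary-care hematocrit or hemoglobin values dated after discharge, labelled as a clinical screen. Without a date rule, the latest value on file could be one from the NICU stay.
- State that 40 treated infants cannot exclude an event of about 1 in 10,000.

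This costs protocol wording only: no extra blood draw, visit or funded test. The downside is that the evaluable number will be small and will be seen to be small. The first-year samples will also come from infants with suspected anemia, so they should be described as a selected group.

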## **MEND (Mild Encephalopathy in the Newborn treated with Darbepoetin)**

11.18.2020

Fauchère and colleagues performed a randomized, double-masked trial in which preterm infants between 24 and 31 weeks GA were given recombinant human EPO (Epoietin Beta in doses of 3000U/kg birth weight) or placebo at 3, 12-18, and 36-42 hours after birth. A multicenter trial looked at preterm infants (26-32 weeks gestation) and found no improvement in neurodevelopmental outcome at 2 years corrected age, and no adverse effects using rhEPO 3000 U/kg.

Once again, **administration of high dose EPO resulted in no significant adverse events(38).**

Regarding the administration of Darbe in preterm infants, Warwood el al showed that a single dose of Darbe accelerated effective erythropoiesis in a pilot study of 12 preterm infants(39). The same group of investigators reported that IV administration to neonates resulted in a shorter half-life, a larger volume of distribution and more rapid clearance(40).

Ohls et al. performed a **randomized, placebo controlled study** to assess the safety and efficacy of **Darbe administered to preterm infants** (500-1250 grams birth weight). In this study they reported preterm infants who received ESAs (Darbe 10 $\mu$ g/kg or EPO 400 U/kg) had significantly better cognitive outcomes at 18-22 months and at preschool testing compared with placebo recipients, with no adverse events reported.(41)

Natalucci et al. recently published a study using prophylactic early high-dose recombinant human erythropoietin in preterm infants (26-31 weeks gestation). 228 participants were randomized to receive either erythropoietin 3000 IU/kg and 220 received the placebo. Erythropoietin was given IV at 3 hours, 12-18 hours, and at 36-42 hours after birth. They found that among infants who received prophylactic erythropoietin there was no significant difference in neurodevelopmental outcome between the groups. No adverse events were reported(42).

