**MEND (Mild Encephalopathy in the Newborn treated with Darbepoetin)**

11.18.2020

Evaluation	Screening	Pre-Entry (Prior to 24 hrs)	Entry (<24 hr of age)	discharge, transfer, or 96 hours of age (which ever occurs first)	3-10 days	Discharge	4 months corrected age	8-12 months corrected age
Screen admissions to NICU	X	X						
Documentation of Gestational Age		X						
Informed Consent		X						
Maternal Demographics and History			X			X		
Blood Pressure			X		X	X		X
Modified Sarnat Exam				X				
MRI as available from clinical care					X	X		
Hematology (CBC/transfusions/phlebotomy loss) as available from clinical care			X			X		X
Administration of study drug IV			X					
Liver/kidney Function Tests (as clinically available)					X			
Complete Physical Exam including weight, head circumference and length			X			X		
Telephone contact to review current status							X	
Ages and Stages phone questionnaire							X	
Phone/in person survey on hospitalizations, seizures, need for respiratory support, failure to thrive, medication use, use of early intervention, hearing impairment, concerns with vision							X	X
Neurodevelopmental assessment Bayley III & Standardized Neurologic exam								X
Weight, length, head circumference, blood Blood pressure, and heart rate								X

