## **8. Risks to Subjects**

Darbe use in adults can increase the risk of abnormal blood clot formation, increase red blood cell number, decrease white blood cell number, increase blood pressure, serious cardiovascular risks, including stroke, venous thrombus, and death. Studies of Darbe use in adult cancer patients have shown increased cancer growth. To date there is no information that these drugs would increase any such complications in infants. There may also be side effects and discomforts that are not yet known.

The infant will be assigned to a treatment group by randomization. The treatment the infant receives might be less effective, not effective, or have more side effects than another study treatment.

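### After discharge, clots, stroke and white-cell or platelet abnormalities are captured only passively, and the back-up request to primary care is worded three different ways

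*Combined protocol and SAP*

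**What the plan says.** **Survey.** The Long Term Safety paragraph (3. Study Design, Safety) plans a 4-month call that adds to the developmental screen questions on "hospitalizations, seizures, need for assisted respiratory support, failure to thrive, medication use, use of early intervention services, hearing impairment, any concern with vision". The follow-up text under PK Sampling gives the same list. The schedule of evaluations marks it at both 4 months and 8-12 months corrected age, in the row that begins "Phone/in person survey on hospitalizations, seizures, need for respiratory support, failure to thrive, medication use".

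**Named risks.** Section 8, Risks to Subjects, says that the drug in adults "can increase the risk of abnormal blood clot formation, increase red blood cell number, decrease white blood cell number, increase blood pressure", and goes on to stroke, venous thrombus and death. The Safety section lists, among events to document in this trial, "neutropenia, thrombotic/vascular events, hematologic events (platelets, Hct level, polycythemia" and blood pressure changes, and gives red cell aplasia its own paragraph. The SAE definition offers major venous thrombosis, stroke and severe hypertension as life-threatening examples.

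**Time windows.** An adverse event counts from dosing to the end of the study period. Targeted safety evaluation stops at day 7 or discharge, whichever is earlier. SAE reporting stops 30 days after therapy or at discharge, whichever is earlier.

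**Primary care.** Long Term Safety says that the study will ask the provider for the child's "medical records and most recent hematocrit/hemoglobin to assess for safety". The text under PK Sampling is permissive: "In addition, we may contact". The list of research-related procedures asks for the records, including hemoglobin and hematocrit, but only where available and indicated.

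**The concern.** The events the protocol itself regards as characteristic of the drug are not the events the follow-up contacts ask about. The survey is a developmental and general-health list. A clot or a low platelet count that comes to light after discharge reaches the data only if a parent volunteers it, if it leads to an admission, seizure or medicine that the parent reports and someone asks why, or if the primary care record is obtained and searched.

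This matters because Section 5, Data Analysis, describes a feasibility trial whose data will support a larger one. If nobody was asked about an event, its absence from the safety table cannot be told apart from a true absence. Uneven collection across the seven centres named under Timeline for the study would add to the problem.

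**Working it through.** No figure in the plan bears on this, so the check sets each named risk against every post-discharge route in the document.

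**Step 1. Coverage by risk.** The survey has 8 items after the developmental screen; 0 of 8 name any of the risks below.

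| Risk | Survey item | Other routes after discharge |
|---|---|---|
| Clot or stroke | None | Primary care records; indirectly, answers on admissions, seizures or medicines |
| White cells, platelets | None | A clinical CBC, if one was done, through the 8-12-month hematology row or the records |
| Red cells, transfusion | None | Latest hematocrit or hemoglobin; hematology and transfusion row at 8-12 months, if clinically available; letter to the provider and leftover blood requested if a CBC is ordered for anaemia in the first year |
| Blood pressure | None | Measured at 8-12 months |

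Clots and stroke have no dedicated route. White cells and platelets have only a passive one. Red cells and transfusion have several partial routes. Blood pressure is measured once. Neither the hematology row nor the blood pressure row is marked at 4 months.

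**Step 2. When active collection stops.** Dosing is before 24 hours of age. Two illustrative discharge times, both taken from time points in the protocol:

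- Discharge at 96 hours (day 4): safety evaluation closes at min(7, 4) = day 4, and SAE reporting at min(about 30, 4) = day 4.
- Discharge at 2 weeks (day 14), a stay that the Safety section calls uncommon: safety evaluation closes at min(7, 14) = day 7, and SAE reporting at min(about 30, 14) = day 14.

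Taking 4 months as 120 days, the interval from the close of SAE reporting to the first scheduled contact is 120 - 4 = 116 days in the first case and 120 - 14 = 106 days in the second. An event in that interval meets the adverse event definition, but it falls outside both active windows and no survey item prompts for it. Actual discharge days are not given, so these are examples.

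**Step 3. How firm the back-up is.**

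- PK Sampling: optional; most recent history and most recent hematocrit.
- Safety, Long Term Safety: definite; records and most recent hematocrit or hemoglobin.
- Research-related procedures list: conditional; records including hemoglobin and hematocrit.
- Schedule of evaluations: no row for the contact.

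A centre can follow the first or third wording and obtain nothing for some infants. Where records do arrive, the text does not say what is to be extracted or for which dates. The laboratory request names one value, the latest, and does not name white cells or platelets. Earlier values may be informative: the Background reports that "a single dose of Darbe accelerated effective erythropoiesis in a pilot study of 12 preterm infants".

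**The case against.** The strongest reply is that the plan collects more than the survey suggests, and much of this stands.

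- A reader who sees only the words "most recent hematocrit/hemoglobin to assess for safety" might infer that primary care is asked for a hematocrit and nothing else. That is not so: the Safety section and the procedures list also ask for medical records, and the PK Sampling text asks for the medical history.
- A reader might infer that late harm goes unrecorded. The 8-12-month blood pressure, the hematology and transfusion row, and the anaemia-triggered sample contradict this. The survey's questions on admissions and medicines could also reveal some serious events.
- A reader might dismiss a hematocrit at 4 months because it lies 120 x 24 / 35 = about 82 half-lives after dosing. A drug half-life does not measure how long a red-cell effect, a clot or aplasia lasts. The 35 h figure comes from day 7, after a second dose, in infants who had been cooled for moderate to severe encephalopathy. A late value is also relevant to red cell aplasia, which the plan follows through the first year. The figure carries no weight here.

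It can also be said that Section 8 takes its risks from adult use and reports no information that they are increased in infants, and that a single-dose trial of 80 infants need not ask about everything. That limits the urgency. It does not remove the mismatch, because the Safety section and the SAE definition adopt these same events as ones to watch for in this trial.

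Finally, the attached questionnaire and the letter to the provider are not in the text available, and the schedule has a 4-month call to review current status whose content is not described. Either could hold a relevant question.

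**Conclusion.** The point holds in a limited form. Post-discharge capture of thrombosis or stroke, and of white-cell or platelet abnormalities, is passive and unprompted. Its main back-up is worded as optional, definite and conditional in three places, with no schedule row, so it may be obtained for only some infants. Late events of these kinds may be missed. The documents do not support saying that they will be, or that all the named risks are uncovered after discharge.

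The size is 0 of 8 survey items on the named risks, both active windows closed by discharge, and three inconsistent wordings. The number of events likely to be missed cannot be estimated, because the documents give neither an expected rate nor an expected completeness of primary care records. The conclusion assumes that the survey asks what the protocol lists and no more. The neurodevelopmental primary outcome is unaffected. The change should be made because it is cheap and removes a contradiction in the safety data collection.

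**What to change.** 1. Add dated yes/no items to the existing 4-month and 8-12-month survey: blood clot or stroke, transfusion, and abnormal blood count. Record the reason for each hospitalisation. If the attached questionnaire already has these, list them in the protocol.
2. Reconcile the primary care wording under PK Sampling, in the research-related procedures list and under Long Term Safety, so that the records request is made for every randomised infant in both arms. Give the contact its own row in the schedule of evaluations.
3. State what is extracted: all dated hematocrit, hemoglobin, platelet and neutrophil values on record since discharge, not only the most recent hematocrit or hemoglobin.

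The cost is a few more questions at contacts already planned and slightly more record abstraction. No visit or blood draw is added.
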